# 2.1.3.2 Secondary efficacy endpoints

# 2.1.3.2.1 Key secondary efficacy endpoints (ITT estimand)

- Percent change in measured LDL-C from baseline to Week 24
- Percent change in non-HDL-C from baseline to Week 12
- Percent change in measured LDL-C from baseline to Week 12
- Percent change in Apo B from baseline to Week 24
- Percent change in Total-C from baseline to Week 24
- Percent change in Lp(a) from baseline to Week 24
- Percent change in TGs from baseline to Week 24
- Percent change in HDL-C from baseline to Week 24
- Percent change in LDL particle number from baseline to Week 24

# 2.1.3.2.2 Diabetes-related endpoints (ITT estimand)

- Absolute change in HbA1c from baseline to Weeks 12 and 24
- Absolute change in FPG from baseline to Weeks 12 and 24
- Absolute change in number of glucose-lowering treatments from baseline to Weeks 12 and 24

### 2.1.3.2.3 Other efficacy endpoints (ITT estimand)

- Percent change in calculated LDL-C from baseline to Weeks 12 and 24
- Percent change in Apo B, Total-C, Lp(a), TGs, HDL-C from baseline to Week 12
- Proportion of patients reaching measured LDL-C <50 mg/dL (1.30 mmol/L), <70 mg/dL (1.81 mmol/L) and <100 mg/dL (2.59 mmol/L) at Weeks 12 and 24
- Percent change in measured LDL-C according to baseline TGs of <median TG or ≥median TG at Weeks 12 and 24
- Proportion of patients reaching non-HDL-C <130 mg/dL (3.37 mmol/L), <100 mg/dL (2.59 mmol/L) and <80 mg/dL (2.07 mmol/L) at Weeks 12 and 24
- Percent change in TGs from baseline to Weeks 12 and 24 according to baseline TGs of <median TG or >median TG
- Percent change in LDL particle number from baseline to Week 12
- Percent change in LDL particle size from baseline to Weeks 12 and 24
- Percent change in VLDL, HDL and IDL particle number from baseline to Weeks 12 and 24
- Percent change in Apo A-1 and Apo C-III from baseline to Weeks 12 and 24

- 26-Apr-2017 Version number: Final
- Absolute change in TGRLs (non-HDL-C minus measured LDL-C if measured LDL-C not missing; non-HDL-C minus calculated LDL-C if measured LDL-C missing and calculated LDL-C not missing, using fasting samples first, or if fasting sample missing using nonfasting measurements) from baseline to Weeks 12 and 24
- Proportion of patients with 50% or greater reduction from baseline in measured LDL-C at Weeks 12 and 24.
- Proportion of patients reaching Apo B <80 mg/dL at Weeks 12 and 24.
- Absolute change in ratio Apo B/Apo A-1, Total-C/HDL-C and LDL-C/HDL-C from baseline to Weeks 12 and 24.

# 2.1.4 Safety endpoints

The safety analysis will be based on the reported AEs and other safety information, such as clinical laboratory data and vital signs.

# Observation period

The observation period will be divided into 3 periods:

- Pre-treatment period is defined from the signed informed consent up to the day before the first dose of open-label alirocumab injection/first dose of usual care treatment for those prescribed another LMT if allocated to the usual care arm. For those allocated to the usual care arm for whom another LMT is not prescribed, the pre-treatment period will end on the day before randomization.
- Treatment Emergent Adverse Event (TEAE) period:
  - o For patients randomized to alirocumab, the TEAE period is defined as the time from the day of the first dose of open-label alirocumab injection to the day of the last dose of open-label alirocumab injection + 70 days (10 weeks) as residual effect of treatment is expected until 10 weeks after the stop of alirocumab.
  - For patients randomized to usual care
    - and who are administered an additional LMT, the TEAE period is defined as the time from the day of the first intake of the usual care drug to 70 days after the day of the last intake or Study Day 225, whichever comes first.
    - and for whom the Investigator has not prescribed an additional LMT, the TEAE period is defined as the time from the day of randomization to the date of the last on-site visit + 70 days, or Study Day 225, whichever comes first.
- Post-treatment period is defined as the time starting the day after the end of the TEAE
  period up to resolution/stabilization of all serious adverse events (SAEs) and AEs of
  special interest (AESI), whichever comes last.

The on-study observation period is defined as the time from the day of the first dose of open-label alirocumab injection/first dose of usual care treatment (for those prescribed another LMT if

allocated to the usual care arm)/randomization (for those allocated to the usual care arm for whom another LMT is not prescribed) until the last protocol planned visit of the patient (Week 32 phone call).

Of note, neither the onset time of AEs nor the time of laboratory samples are collected in the clinical database. As a consequence it is not possible for AEs and potentially clinically significant abnormalities (PCSAs) starting the first day of the TEAE period to know if they occurred before or after the first intake of IMP. By definition of the TEAE period, they are considered to be treatment emergent even if, for example in the case of PCSA, it is not likely because laboratory samples must be collected before randomization (and thus drug administration) as per protocol.

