The data on lipid parameters from blood samples will be masked after randomization. No attempts should be made by the Investigator or patient to have the patient's lipid values independently evaluated after randomization until after the Week 24 visit, except for the safety of the patient as per the Investigator's judgment. At the end of the OLTP (Week 24 visit), the Investigator will continue to manage the patient's lipids in accordance with standard practice. Any lipid values after randomization (eg, if done for patient safety) should be redacted in the source documents and not shared with the Sponsor.

Duration of study treatment will be 24 weeks with the last injection of open label alirocumab administered at Week 22. The treatments prescribed in the usual care arm will be administered for 24 weeks. From the Week 24 visit onward, the Investigator will continue to manage the patient's lipids in accordance with standard practice.

Patients will visit the study site at Weeks -3, 0, 8, 12, 20, and 24 with lab work at each visit; in addition a phone visit is scheduled at Weeks 4 and 32. Week 8 is a critical visit because it will be the only scheduled visit where a non-HDL-C value for uptitration will be available.

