## 10.1.2.5 Week 32 / 10 weeks after last alirocumab injection (phone call)

- Record concomitant medication, noting also whether the patient has started a commercially available PCSK9 inhibitor
- Record statin treatment, as applicable

• Collect information on AEs (if any)

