# • Local injection site reactions:

- o deemed to be allergic by the Investigator (or have an allergic component) AND that require consultation with another physician AND related to alirocumab (as opposed to another injectable) AND selected using the following selection of PTs from the safety complementary form for local injection site reaction or from the reported term {"Injection (infusion) site dermatitis", "Injection (infusion) site hypersensitivity", "Injection (infusion) site oedema", "Injection (infusion) site rash", "Injection (infusion) site urticaria", "Injection (infusion) site eczema", "Injection (infusion) site vasculitis", "Injection (infusion) site swelling"};
- o in addition, an analysis will be performed for any local injection site reaction not meeting AESI criteria (not allergic and not requiring consultation with another physician) but meeting the above criteria AND related to alirocumab (as opposed to another injectable).
- Pregnancy of female patient (including male patient's partner) selected using appropriate MedDRA codes.
- Symptomatic overdose with alirocumab:
  - an overdose with alirocumab is defined as at least twice of the intended dose within the intended therapeutic interval (i.e., 2 or more injections are administered in <7 calendar days), to be reported using the term "symptomatic OVERDOSE" (accidental or intentional), indicating the circumstance in parentheses (e.g., "symptomatic overdose [accidental]" or "symptomatic overdose [intentional]"). These events will be selected using the AESI category as selected by the site.
  - in addition, another analysis will be performed analysing all overdose cases (whether symptomatic or asymptomatic) related to alirocumab using the HLT for overdose.

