# 2.3.2 Safety population

The safety population considered for safety analyses will be the randomized population who did actually receive at least one dose or part of a dose of the open-label alirocumab and all patients randomized to usual care.

Patients will be analyzed according to the treatment actually received (usual care or alirocumab).

The safety analysis will focus on the TEAE period defined in Section 2.1.4.

In addition:

- Non-randomized but treated patients or patients treated before the randomization will not be part of the safety population, but their safety data will be presented separately;
- Randomized patients for whom it is unclear whether they took the study medication will be included in the safety population as randomized;
- For patients receiving more than one study treatment during the trial, the treatment group allocation for as-treated analysis will be the one to which the patient was treated with the longest duration.

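### Adverse events that begin after a usual-care patient starts a commercial PCSK9 inhibitor between Week 24 and Day 225 count as usual-care events, and no SAP rule separates them

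*SAP*

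**What the plan says.** SAP 2.1.4 (Observation period) defines three treatment-emergent windows:

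- Alirocumab: first injection "to the day of the last dose of open-label alirocumab injection + 70 days (10 weeks").
- Usual care with an added lipid-modifying drug: first intake "to 70 days after the day of the last intake or Study Day 225, whichever comes first".
- Usual care without one: randomization "to the date of the last on-site visit + 70 days, or Study Day 225, whichever comes first".

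Protocol 8.8.3 prohibits other PCSK9 inhibitors only up to the end-of-treatment visit. Protocol 6.1 then says: "From the Week 24 visit onward, the Investigator will continue to manage the patient's lipids in accordance with standard practice". At the Week 32 call (Protocol 10.1.2.5) the site records concomitant medication, "noting also whether the patient has started a commercially available PCSK9 inhibitor".

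SAP 2.3.2 sets the safety allocation: "Patients will be analyzed according to the treatment actually received (usual care or alirocumab"). A patient who received more than one study treatment goes to the one taken longest. SAP 2.4.5.1 uses the whole safety population as the denominator of adverse event percentages. It plans patient-year rates and, for selected events, Kaplan-Meier curves and hazard ratios against usual care. Event-free patients are censored at the end of the treatment-emergent period.

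**The concern.** The usual-care window stays open for eight weeks after the restriction on the test drug class has been lifted. Nothing in SAP 2.1.4, 2.3.2 or 2.4.5.1 ends, censors or flags usual-care time when a commercial PCSK9 inhibitor is started. The longest-duration rule does not help. It concerns study treatments, and 24 weeks of usual care outweighs at most 8 weeks of a commercial product in any case.

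A usual-care patient who starts such a product soon after Week 24 and then has an allergic reaction to it is reported as a usual-care event. For events that the class increases, the control rate rises and the difference between arms shrinks, which in a safety comparison can mask a signal. The analyses exposed are the crude incidence tables, the patient-year rates, the Week 32 Kaplan-Meier incidence and the hazard ratios.

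The SAP deals with the same issue for efficacy. SAP 2.4.4.1.3 treats the addition of a new lipid-modifying drug as a treatment change in both groups and runs a sensitivity analysis without the later values. Safety has no counterpart.

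**Working it through.** **Step 1. Reproduce the plan's dates.** Study day = 1 + 7 × week.

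- Last planned injection ("last injection of open label alirocumab administered at Week 22"): 1 + 7 × 22 = Day 155.
- End of randomized treatment, Week 24: 1 + 7 × 24 = Day 169.
- Week 32 call: 1 + 7 × 32 = Day 225.
- Alirocumab completer: 155 + 70 = Day 225. This reproduces the plan's equation of Week 32 with 10 weeks after the last injection.

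**Step 2. End of the usual-care window.**

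- Completer with an added drug: min(169 + 70, 225) = min(239, 225) = Day 225.
- Completer without one, last on-site visit Day 169: also Day 225.
- Any last intake on or after Day 155 gives Day 225 (225 − 70 = 155).
- A last intake on or before Day 99 closes the window by Day 169 (169 − 70 = 99), so there is no overlap.

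**Step 3. Overlap with permitted PCSK9 inhibitor use.** 225 − 169 = 56 days; 56 / 225 = 24.9% of a completer's window.

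**Step 4. Person-time.** The planned usual-care arm is about 140 patients, or 140 × 225 = 31,500 patient-days. Uptake is not in the documents, so the values below are assumptions. Starting everyone on Day 169 gives the upper limit.

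| Assumed uptake | Starters | Patient-days (× 56) | Share of 31,500 |
|---|---|---|---|
| 5% | 7 | 392 | 1.2% |
| 10% | 14 | 784 | 2.5% |
| 20% | 28 | 1,568 | 5.0% |

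**Step 5. Injection-site events.** Protocol section 4 gives 6.2% on alirocumab and 4.2% on control in the pooled studies.

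- Applying 6.2% in full: 7 × 0.062 = 0.4 to 28 × 0.062 = 1.7 patients.
- Applying the difference, 6.2 − 4.2 = 2.0 points: 7 × 0.02 = 0.14 to 28 × 0.02 = 0.56 patients.

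The first line is an upper bound. The overlap is at most 8 weeks, some of the alirocumab studies ran up to 78 weeks, and starters may take a PCSK9 inhibitor other than alirocumab.

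**The case against.** **The common end date is deliberate.** Day 225 is where the alirocumab window also ends for completers, so the arms have equal observation time. This stands, and it is the reason to keep Day 225 for the crude tables. A reader might infer that usual-care windows should simply be cut at the first commercial dose. Under SAP 2.4.5.1, starters would stay in the denominator while their later background events left the numerator, which would lower the usual-care percentages artificially.

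**The tail itself.** A reader might also set the 70 days against the 3 days that SAP 2.4.4.1.3 allows after the last dose of a usual-care drug. That figure is an imputation assumption for non-HDL-C and says nothing about attributing adverse events.

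**Crossover is not shown to be expected.** The Week 32 question is put to both arms, and investigators are masked to post-randomization lipids through Week 24. This stands: the documents show that starts are permitted and recorded, not how many there will be.

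**Much is already visible or unaffected.** Concomitant lipid drugs are tabulated by group, all serious events are listed, scheduled safety laboratory tests end at Week 24, and a Kaplan-Meier estimate at Week 24 is not changed by later events. This limits the problem. It does not reach the Week 32 incidence, the hazard ratios, the patient-year rates or the crude tables.

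**Injection-site reactions.** The main SAP 2.1.4.1 groupings require the event to be "AND related to alirocumab (as opposed to another injectable"). A reader might infer that the hazard ratio is a product of crossover and that censoring would repair it. It would not: without crossover the usual-care count is zero by definition, apart from protocol deviations, and the ratio cannot be estimated. That is a separate fault of the definition. SAP 2.1.4.1 also gives a second approach through the e-CRF drop-down.

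**Conclusion.** The gap is real. As written, events that begin on a commercial PCSK9 inhibitor after Week 24 are usual-care treatment-emergent events for up to 56 days, whether or not a lipid drug was added at randomization.

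The effect is probably small: at most about 1.2-5.0% of usual-care person-time and probably fewer than 2 injection-site events. These figures rest on an assumed uptake of 5-20%, starts at Day 169, and the pooled 6.2% rate applied in full to a short exposure.

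A reader might infer that the bias always favors alirocumab. The documents support that direction only for events that the class increases; Protocol section 4 reports similar overall percentages of adverse events, serious events and discontinuations. All of this concerns descriptive safety, and no efficacy result is affected. The change is worth making because it is inexpensive and the hazard ratios would otherwise mix exposures without saying so.

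**What to change.** Keep the Day 225 window for the main crude tables. Add to SAP 2.4.5.1:

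- (a) Censor usual-care patient-year rates, Kaplan-Meier curves and hazard ratios at the day before the first commercial PCSK9 inhibitor dose, as recorded on the lipid-modifying therapy medication page.
- (b) Flag and list usual-care adverse events with onset on or after that first dose.
- (c) Add a table of treatment-emergent events to Week 24 (Day 169) for both arms.
- (d) If the start date is missing, treat the patient as a starter from the day after the Week 24 visit. SAP 2.5.2 does not impute medication dates, so state this as an exception for classification only.
- (e) Report no hazard ratio for injection-site reactions defined as related to alirocumab, because usual-care patients cannot meet that definition on randomized treatment.

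The cost is SAP wording and one extra table and listing. SAP 2.1.2 already has all medications reported until the end of the study, so no new data item is needed; the Week 32 question alone asks whether, not when. The downside is that a few patient-weeks of usual-care follow-up leave the time-based analyses, and that censoring at a treatment decision may be slightly informative. The uncensored crude tables and the Week 24 table let the reader judge both.

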# 9.2.3 Safety endpoints

Safety parameters (AEs, laboratory parameters, vital signs) will be assessed throughout the study.

The observation of safety data will be as follows:

- Pre-treatment period is defined from the signed informed consent up to the first dose of open-label alirocumab injection/first dose of usual care treatment for those prescribed another LMT if allocated to the usual care arm. For those allocated to the usual care arm for whom another LMT is not prescribed, the pre-treatment period will end on Day 1 at the time of randomization.
- Treatment Emergent Adverse Event period is defined as the time from the first dose of open-label alirocumab injection to the last dose of open-label treatment + 70 days (10 weeks) as residual effect of treatment could be expected until 10 weeks after the stop of alirocumab. For patients randomized to usual care, this will be considered as 70 days after the last usual care treatment (IMP) has been administered, or Study Day 225, whichever comes first. For patients who are randomized to usual care and the Investigator has not prescribed an additional LMT, the "date of last dose of usual care" is defined as the date of the last on-site visit.
- Post-treatment period is defined as the time starting the day after the end of the TEAE period up to resolution/stabilization of all SAE and AESI, whichever comes last.

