#### 1.4 STUDY PLAN

This is a Phase 3b/4 randomized, open-label, parallel group study to assess the efficacy and safety of alirocumab administered by subcutaneous injection versus usual care in patients with Type 2 diabetes and mixed dyslipidemia at high CV risk with non-HDL-C not adequately controlled with maximally tolerated statin therapy. The study will be multinational and multicenter. The study consists of a screening period of up to 3 weeks, an open-label treatment period (OLTP) of 24 weeks, and a safety observation period of 8 weeks.

Patients, unless they are statin intolerant, will be taking a stable, maximally tolerated dose of statin therapy without other LMTs. Statin dose and dose regimen should be stable throughout the entire study duration including for 4 weeks prior to the screening period and from screening to the end of the OLTP. Patients should continue to follow a cholesterol lowering diet during the study, however, the Investigator may reinforce diet recommendations according to local/regional guidelines. Patients should be receiving treatment for diabetes in accordance with local/regional standards of care. Changes to antihyperglycemics should be limited and made only in circumstances where it is clinically needed.

The usual care arm includes the option to continue on the maximum dose of statin that is tolerated by the patient without the addition of a new LMT at randomization, or may initiate either ezetimibe, fenofibrate, omega-3 fatty acids, or nicotinic acid at randomization for the remainder of the 24-week treatment period. Initiation of usual care treatment should start as soon as possible after randomization, but no later than 7 days from the day of randomization.

The Investigator will select the most appropriate LMT for the patient prior to randomization (consisting of either no additional LMT but continuing on maximum tolerated statin, ezetimibe, fenofibrate, omega-3 fatty acids or nicotinic acid) and enter this information into the IVRS. If the patient is randomized to open-label alirocumab, the Investigator will not institute the LMT option that was selected and entered into IVRS but instead treat the patient with open-label alirocumab. If the patient is randomized to usual care (non-alirocumab), the Investigator will initiate treatment with the LMT option that was selected and entered into IVRS, as applicable, in addition to continuing the patient on the maximum tolerated dose of statin.

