# 2 STATISTICAL AND ANALYTICAL PROCEDURES

### 2.1 ANALYSIS ENDPOINTS

The baseline value is defined generally as the last assessment obtained before the first injection of open-label alirocumab/first dose of usual care treatment or before randomization for patients randomized to usual care and not receiving additional LMT. All laboratory assessments taken the day of randomization will be considered as being performed prior to the first investigational medicinal product (IMP) administration.

All baseline safety and efficacy parameters (apart from those listed below) are presented along with the summary statistics in the safety and efficacy sections (Section 2.4.5 and Section 2.4.4).

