#### General common rules

All safety analyses will be performed on the safety population as defined in Section 2.3.2, unless otherwise specified, using the following common rules:

- Safety data in patients who do not belong to the safety population (e.g., exposed but not randomized or re-randomized patients) will be listed separately.
- The baseline value is defined generally as the last available value before the first injection of open-label alirocumab/first dose of usual care treatment for patients prescribed another LMT if allocated to the usual care arm/ randomization for patients randomized to usual care and not receiving additional LMT.
- The PCSA values are defined as abnormal values considered medically important by the Sponsor according to predefined criteria/thresholds based on literature review and defined by the Sponsor for clinical laboratory tests and vital signs (PCSA version dated January 2009 [Appendix A]).
- PCSA criteria will determine which patients had at least one PCSA during the TEAE period, taking into account all evaluations performed during the TEAE period, including nonscheduled or repeated evaluations. The number of all such patients will be the numerator for the on-treatment PCSA percentage.
- The treatment-emergent PCSA denominator by group for a given parameter will be based on the number of patients assessed for that given parameter in the TEAE period by treatment group on the safety population.
- All measurements, scheduled or unscheduled, fasting or not fasting, will be assigned to analysis windows defined in Section 2.5.3 in order to provide an assessment for Week 0 to Week 24 time points.
- For quantitative safety parameters based on central laboratory measurements, descriptive statistics will be used to summarize results and change from baseline values by visit and treatment group using analysis windows. Summaries will also include the last on-treatment value and the worst on-treatment value. The last on-treatment value is defined as the last value collected during the treatment period (see Section 2.1.4). The worst on-treatment value is defined as the nadir and/or the peak value during the treatment period according to the direction (minimum or maximum) of the abnormality as defined in the PCSA list.
- For exploratory purpose, all TEAE analyses will be provided according to up-titration status, i.e., according to whether the patients remained on the 75 mg dose or whether they

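### A randomisation-day lab that the SAP deems pre-dose is also counted as a treatment-emergent PCSA, except in usual-care patients who start LMT on Days 2-8

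*SAP*

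**What the plan says.** **Baseline.** SAP 2.1 takes baseline as the last assessment before the first dose, or before randomisation for usual care with no added LMT. It then fixes the order for labs: "All laboratory assessments taken the day of randomization will be considered as being performed prior to the first investigational medicinal product (IMP) administration".

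**Start of the TEAE period.** Under SAP 2.1.4 the period opens on the day of first injection for alirocumab and on the day of randomisation for usual care without added LMT. For usual care with an added LMT, "the TEAE period is defined as the time from the day of the first intake of the usual care drug". SAP 1.4 allows that LMT to start after randomisation, "but no later than 7 days from the day of randomization".

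**First-day events.** SAP 2.1.4 notes that neither AE onset times nor lab sample times are in the database. Of AEs and PCSAs on the first day of the period it says: "By definition of the TEAE period, they are considered to be treatment emergent even if, for example in the case of PCSA". The rest of that sentence grants that emergence is unlikely, because the protocol requires samples before randomisation and hence before drug.

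**PCSA counts.** Under the general rules of SAP 2.4.5 the numerator is formed by "taking into account all evaluations performed during the TEAE period, including nonscheduled or repeated evaluations", and the denominator is "based on the number of patients assessed for that given parameter in the TEAE period". Neither rule leaves out the baseline sample. SAP 2.4.5.3 tabulates lab PCSAs regardless of baseline level and/or by baseline status (normal or missing, abnormal).

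**The concern.** The SAP gives one blood sample two incompatible roles. For choosing a baseline it is pre-dose; for counting abnormalities it is on treatment. Uncollected sample times explain the second rule for AEs, where the order of onset and dose is truly unknown. They do not explain it for labs. SAP 2.1 has already settled the lab order without needing times, and Protocol 10.1.2.1 puts the first injection only after the fasting draw.

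Two things are at stake:

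- A value that the SAP itself treats as pre-dose can be reported as a treatment-emergent abnormality.
- The rule depends on when treatment starts, and only usual-care LMT has a planned start window beyond Day 1. The two arms can therefore be counted differently.

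**Working it through.** There is no planned figure to reproduce. The check applies the SAP rules as written to a Day 1 lab.

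**Inputs.** Day 1 is the day of randomisation (SAP 2.5.3). The latest permitted LMT start is Day 1 + 7 = Day 8 (SAP 1.4). The first alirocumab injection is at the randomisation visit, after sampling (Protocol 10.1.2.1). Planned arm sizes are 280 and 140 (SAP 1.1).

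**Step 1: who has the Week 0 lab counted.** It is counted if the first TEAE day is Day 1.

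| Group | First TEAE day | Week 0 lab counted |
|---|---|---|
| Alirocumab, injected Day 1 | 1 | yes |
| Usual care, no added LMT | 1 | yes |
| Usual care, LMT started Day 1 | 1 | yes |
| Usual care, LMT started Days 2-8 | 2-8 | no |

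**Step 2: which labs are drawn at Week 0.** The flow chart (Protocol 1.2) has fasting glucose and HbA1c in every patient. Other safety labs are repeated only after a clinically relevant abnormal screening value, so those samples are selected for abnormality. Scheduled samples that can yield a treatment-emergent PCSA, Day 1 starters against later starters:

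- Glucose: Weeks 0, 8, 12, 24 = 4, against 3.
- HbA1c: Weeks 0, 12, 24 = 3, against 2.

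**Step 3: which outputs are affected.**

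- Criteria that also need a change from baseline (SAP 2.5.2) are not. A sample that is its own baseline has change 0.
- The normal-at-baseline row is not, because an abnormal Week 0 baseline puts the patient in the other row.
- The liver displays are not. SAP 2.4.5.3 uses post-baseline visits for the liver PCSA table and post-baseline values for eDISH.
- The row regardless of baseline level is affected for any threshold-only criterion.
- The abnormal-at-baseline row, if produced, is affected more. Take a Day 1 starter whose baseline is the Week 0 sample. Abnormal at baseline means that sample crosses the threshold, and the same sample is in the numerator. The row is 100% by construction for such patients, whatever happens later.

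**Step 4: between-arm effect in the row regardless of baseline.** Let q be the share of patients with a Week 0 PCSA that does not recur, and u the share of usual-care patients who start LMT on Days 2-8. Assume q is the same in late starters as in the rest, alirocumab is injected on Day 1, and all patients have later samples, so that denominators match.

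- Alirocumab excess from Week 0 alone: q.
- Usual-care excess: q(1 - u).
- Difference: q - q(1 - u) = u x q.

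This is never negative, so it runs against alirocumab. It is zero when u = 0, and both arms are then inflated equally by q. It cannot exceed q. The documents give neither u nor q. For scale, each late starter with a Week 0-only abnormality lowers the usual-care percentage by 1/140 = 0.7 points relative to counting that patient as Day 1 starters are counted.

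**Step 5: denominator.** A patient whose only value is at Week 0 enters the denominator as a Day 1 starter but not as a late starter.

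**Step 6: after the fix.** With Week 0 labs excluded everywhere, the Week 0-only contribution is 0 in both arms and the difference is 0 for any u and q.

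**The case against.** The best defence is that the convention is open and deliberate. The SAP states it, says why, and concedes that emergence is unlikely. Choosing a baseline and classifying events are different tasks, and inclusive counting protects against a sample drawn after dosing that nobody could detect. Any between-arm distortion counts against alirocumab, the analyses are descriptive, and the liver and normal-at-baseline displays are already protected.

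The points about size and direction stand. The defence of the rule does not, for labs. SAP 2.1 already assumes that no randomisation-day lab follows dosing, so the inclusive rule guards against something the SAP has ruled out. It also does so unevenly, and it leaves the abnormal-at-baseline row uninformative for Day 1 starters.

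Some stronger readings are tempting but not supported:

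- *The SAP contradicts the protocol on the periods.* Protocol 9.2.3 says "Pre-treatment period is defined from the signed informed consent up to the first dose of open-label alirocumab injection/first dose of usual care treatment" and, with no added LMT, "the pre-treatment period will end on Day 1 at the time of randomization". The SAP closes the pre-treatment period the day before. That is a day-level version of the same rule for a database without times; it is not a conflict of substance.
- *Week 0 vital signs show the same contradiction.* The SAP 2.1 sentence covers labs only. That vital signs precede dosing is inferred from the order of the visit procedures and from the blood-pressure exclusion (E 08). The baseline-status split in Protocol 11.4.3.2 is optional, so its absence for vital signs in SAP 2.4.5.4 is no breach.
- *Last and worst on-treatment values are contaminated.* SAP 2.4.5 ties these to a treatment period that SAP 2.1.4 does not separately define, so this cannot be shown.

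**Conclusion.** The inconsistency holds for randomisation-day labs and is minor. The wording conflict is certain; its effect on any table is conditional. It needs a threshold-only criterion for a lab drawn at Week 0, and Appendix A is not available to confirm one. Fasting glucose and HbA1c are candidates because everyone has them, as are labs repeated after abnormal screening values.

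Where such a criterion exists, a baseline value can be reported as treatment-emergent. The abnormal-at-baseline row, if produced, is 100% by construction for Day 1 starters whose baseline is that sample. The between-arm effect is u x q under the assumptions stated, of unknown size, zero if all LMT starts on Day 1 and otherwise against alirocumab.

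A reader might infer a hidden safety signal or a threat to the trial's error rates. Neither follows: the direction inflates the alirocumab count, and no formal safety test is planned.

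**What to change.** Keep the SAP 2.1 sentence and apply it throughout. In SAP 2.4.5, state that randomisation-day lab values are excluded in every group from treatment-emergent lab PCSA numerators and denominators, so that only post-baseline values count, as SAP 2.4.5.3 already does for eDISH. Amend the PCSA part of the note in SAP 2.1.4 to match. Leave AE classification as it is, since onset times really are unknown.

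Extending the same filter to Week 0 vital signs and to last and worst values would be tidy but is optional.

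The cost is two or three SAP sentences and one filter in the PCSA programs, with no new data. The downside is that a randomisation-day lab actually drawn after dosing would not be counted, which SAP 2.1 already assumes does not occur.
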